Aim 2 - Estimation of effect sizes for calculating sample size for future R01: Analyses for Aim 2 of the pilot/feasibility study will focus on estimation of preliminary effectiveness as determined by: (a) change in quality of life; (b) change in self-management; and (c) change in disease activity (self-reported). Estimates of effect sizes for outcome variables will be reported as point estimates (mean differences between pre-post measures, as appropriate) and interval estimates (95% CI) to provide a preliminary indication of the presence of a clinically important treatment effect.[201-203] After studying the distributions of baseline characteristics, we will use a linear mixed-effects regression model to estimate the difference in the change from baseline between the two groups. Least squares means for each outcome variable will be compared at the primary time point (week 12) and at intermediate time points (week 6 or 12) using model contrasts to estimate the corresponding 95% CI for the estimates of the difference in outcome means (effect sizes) between and within treatment group.

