
Sample Size Justification: The primary goal in Aim 1 is to estimate the proportion of participants who are compliant in the two groups. A sample of 20 subjects per group provides a 95% confidence interval for compliance within group with a width < 0.46 assuming at least 50% compliance. Compliance is anticipated to be greater than 50% which will yield a more precise estimate. The primary goal in Aim 2 is to estimate the change in LUP-QOL between baseline and 12 months post intervention within and between each treatment. Mean change from baseline with group and the difference in change between groups will be estimated using contrast statements from a linear mixed model of LUP-QOL score with fixed effects for treatment, time, and the treatment by time interaction and a random subject effect. A sample of 20 participants measured at 3 time points and assuming an AR(1) correlation with $\rho=0.5$ allows us to estimate a two-sided 95% confidence interval for change in LUP-QOL from baseline within group to within 0.57 standard deviations (1). A sample size of 20 subjects per treatment group also allows us to estimate a 95% confidence interval for the difference in change in LUP-QOL from baseline between the two groups to within 0.64 standard deviations from the mean assuming common standard deviation between the groups.

E. PROTECTION OF HUMAN SUBJECTS

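### The Aim 2 wording leaves two between-arm contrasts that could be taken as the effect size for the future R01; one baseline-adjusted week-12 contrast should be named

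*Protocol*

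**What the plan says.** The relevant paragraph of the Analysis Plan is headed "Aim 2 - Estimation of effect sizes for calculating sample size for future R01", so its estimates have a declared use. It frames effectiveness as change in three domains (quality of life, self-management, self-reported disease activity) and describes effect sizes as pre-post mean differences where appropriate. It then gives the between-arm analysis: "we will use a linear mixed-effects regression model to estimate the difference in the change from baseline between the two groups".

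The following sentence compares least squares means for every outcome at week 12, the primary time point, and at intermediate times. It promises intervals "for the estimates of the difference in outcome means (effect sizes) between and within treatment group".

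The Sample Size Justification covers LUP-QOL only. Its stated goal for Aim 2 is change, within and between treatments, and it says that "the difference in change between groups will be estimated using contrast statements from a linear mixed model of LUP-QOL score". The model has fixed effects for treatment, time and their interaction, plus a random subject effect. The response is the score at three time points, so baseline is part of the response, and no baseline covariate is named. The section gives half-widths of 0.57 SD for within-group change and 0.64 SD for the between-group difference in change.

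**The concern.** In a model with baseline in the response, the difference in change is the treatment-by-time interaction at week 12. The difference in week-12 least squares means is the treatment main effect plus that interaction. These are two contrasts with different values, variances and natural standardising SDs. Aim 2 mentions both within two sentences and attaches the effect-size label to wording that can be read as the second.

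The stated product of Aim 2 is a number that will size a later trial. If the plan does not fix which contrast supplies it, the reported value depends on chance baseline imbalance and on a choice that could be made after both results are known. There is also a precision cost: neither contrast as written uses baseline efficiently.

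**Working it through.** **Inputs.** From the Sample Size Justification: 20 per arm, AR(1) with correlation 0.5, common SD, two-sided 95% intervals. With assessments at baseline, week 6 and week 12, baseline to week 12 is lag 2, so the correlation is 0.5² = 0.25. Complete data and randomised arms are assumed. The unit is the outcome SD.

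**The plan's own figures.**
- Within-group change: per-subject variance 2(1 − 0.25) = 1.5. Half-width = t(19) × √(1.5/20) = 2.093 × 0.274 = 0.573. This matches 0.57.
- Between groups: t(38) × √(2/20) = 2.024 × 0.316 = 0.640. This matches 0.64, but only with a per-subject variance of 1.
- Difference in change on the same scale as the 0.57: t(38) × √(2 × 1.5/20) = 2.024 × 0.387 = 0.784.

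So the 0.64 fits difference in change only if its unit is the SD of change or the baseline to week-12 correlation is 0.5. It also equals the half-width for the unadjusted week-12 difference in outcome SDs. The two printed figures are therefore not on one scale under the stated AR(1) assumption, and the standardising SD needs stating too.

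**Gap between the contrasts.** Let D0 and D12 be the between-arm differences in mean at baseline and week 12.
- Week-12 contrast: D12, variance 2/20 = 0.10.
- Difference in change: D12 − D0, variance 2 × 1.5/20 = 0.15.
- Gap: D0, variance 2/20 = 0.10, SD 0.316.
- P(|gap| > 0.3) = 2[1 − Φ(0.3/0.316)] = 0.34. The same formula gives 0.53 for a gap above 0.2 and 0.11 above 0.5.
- Covariance 0.10 − 0.25 × 0.10 = 0.075, so correlation = 0.075/√(0.10 × 0.15) = 0.61.
- With a true effect of 0.3 SD (assumed), simulation gives a mean of 0.300 for both, and opposite signs in about 20% of datasets.

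**Consequence for the R01.** Assume 80% power and two-sided 0.05. Then n per arm = 2 × (1.960 + 0.842)² × variance/δ² = 15.70 × variance/δ². Suppose the pilot shows D12 = 0.5 and D0 = 0.2.
- Week-12 contrast: δ = 0.5, variance 1, giving 63 per arm.
- Difference in change: δ = 0.3, variance 1.5, giving 262 per arm.

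**Adjusting for baseline.** The estimate is D12 − 0.25 × D0, with variance 2(1 − 0.25²)/20 = 0.094. Half-width = 2.024 × 0.306 = 0.62. In the example, δ = 0.5 − 0.05 = 0.45 with per-subject variance 0.9375, giving 73 per arm. Relative to difference in change the variance ratio is 0.094/0.15, about 0.63.

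**The case against.** The strongest reply is that the protocol does choose. The Sample Size Justification makes change the Aim 2 goal for LUP-QOL and names difference in change as the contrast. Aim 2 frames all three domains as change. The interval in the last sentence may simply refer back to the difference in change. The effect-size label also covers within-group differences, which can only be changes over time. Much of this stands: for LUP-QOL the plan leans clearly one way, and a reader who inferred that nothing indicates the intended contrast would be wrong. It does not settle the matter for the Patient Activation Measure or the Systemic Lupus Activity Questionnaire. Nor does it remove the week-12 comparison of means for every outcome, which the same sentence describes.

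A reader might also infer that the plan produces biased or inflated results. It does not follow. If the more favourable of the two estimates were always reported, at least one interval would exclude zero in about 9% of null trials. With a true effect of 0.3 SD, the chosen estimate would average about 0.43 SD. The protocol describes no such practice, and Aim 2 plans estimation without a significance test or go/no-go rule. Under randomisation each contrast used consistently is unbiased.

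Two further limits apply. The protocol speaks of least squares means, not raw means; these coincide only with complete data and no covariates. And 0.3 SD is only a yardstick here: the Background reports PALS effect sizes above 0.3, from an uncontrolled pre-post pilot, which is not a between-arm estimate.

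Exact contrast coding can be left to an analysis plan. The point here is that the protocol's own sentences admit two contrasts.

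**Conclusion.** The point holds as a should-fix matter of clarity and precision. The Aim 2 wording admits two between-arm contrasts as the effect size for the R01, mainly for outcomes other than LUP-QOL. Under the stated model they differ by the baseline imbalance, SD about 0.32 outcome SD at 20 per arm. Difference in change, the contrast the plan favours, is also the less precise option: half-width 0.78 outcome SD against about 0.62 after baseline adjustment.

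These figures assume the plan's AR(1) correlation of 0.5, common SD, complete data and chance-only imbalance. The last assumption depends on allocation, where the protocol disagrees with itself. The Recruitment of SLE patients section and the consent section under Protection of Human Subjects say that patients are randomised. The Overview of Study Design compares patients who agree to phone sessions with those who opt for questionnaires only. If arms are self-selected, baseline differences are not chance, and the two contrasts need not target the same quantity.

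**What to change.** First reconcile the allocation wording in the Overview of Study Design with the randomisation stated elsewhere.

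If arms are randomised, in both Aim 2 and the Sample Size Justification:
- name one between-arm effect size per outcome, the week-12 difference adjusted for baseline (baseline as covariate, or a model with a common baseline mean across arms, under which the week-12 difference and the difference in change coincide);
- state the standardising SD and give one 95% CI;
- label unadjusted week-12 means and within-arm changes as descriptive, and move the effect-size label to the named contrast;
- restate the between-group precision for that contrast in a declared SD unit (about 0.62 outcome SD on the present assumptions).

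If arms turn out to be self-selected, do not constrain baselines to be equal. Keep one named contrast and report it as a non-randomised comparison.

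The cost is a few sentences in two sections, with no added data, staff or patients. The team gives up the freedom to choose between contrasts later.

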Overview of Study Design. The Care-coordination Approach to Learning Lupus Self-Management (CALLS) study is a double arm, pre-post pilot designed to examine whether modeling and reinforcement from a lay patient navigator/care coordinator improves disease self-management, indicators of disease activity, health related quality of life (HRQOL), and 30-day readmission in SLE inpatient admissions. We will recruit 40 patients (20 questionnaires and phone sessions and 20 questionnaires only) with active SLE upon hospital admittance at the Medical University of South Carolina (MUSC). The lay patient navigator/care coordinator will be trained to deliver intervention content by twelve weekly telephone sessions carried out across the course of the study. All participants will be assessed using validated measures of patient reported outcomes at baseline, mid-intervention (6 weeks post-enrollment), and immediately following the intervention (12 weeks post-enrollment). Outcomes for patients who agree to phone sessions will be compared with the outcomes of patients who opt to participate in questionnaires only. The study will last 12 months with recruitment and enrollment over 6 months, 3 months for intervention delivery and 3 months for data analysis.

Study Population. The total number of individual patients with systemic lupus erythematosus (SLE) currently being followed by clinicians at MUSC is 1,159 in the past six months that had this encounter diagnosis and 1,526 with this diagnosis in the chart history or problem list or encounter diagnosis, of which approximately 60% are African American and 90% are female. This will allow for the assessment of impact and cost savings/effectiveness according to underrepresented racial and gender categories. The target population for this study will be SLE inpatient admissions. There are approximately 35 SLE and Scleroderma hospital admissions each month, so it is expected that over a 3-month recruitment period, we will be able to recruit 40 participants (20 questionnaires and phone sessions and 20 questionnaires only).

Recruitment of Lay Patient Navigator/Care Coordinator

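### The Aim 2 model leaves baseline LUP-QOL unadjusted, giving a half-width of 0.78 SD instead of about 0.62 SD, and its covariance, read literally, conflicts with the planned AR(1)

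*Protocol*

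**What the plan says.** The Aim 2 model is set out in the protocol, section D, Sample Size Justification: "a linear mixed model of LUP-QOL score with fixed effects for treatment, time, and the treatment by time interaction and a random subject effect". Change within and between groups is taken from contrasts of this model, so baseline is one of the responses and each arm has its own baseline mean.

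Precision is then planned on a named correlation pattern: "A sample of 20 participants measured at 3 time points and assuming an AR(1) correlation with $\rho=0.5". The within-group claim is that this "allows us to estimate a two-sided 95% confidence interval for change in LUP-QOL from baseline within group to within 0.57 standard deviations". The between-group claim, again with 20 per arm, is an interval "to within 0.64 standard deviations from the mean assuming common standard deviation between the groups".

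The Analysis Plan for Aim 2 agrees on the target: "we will use a linear mixed-effects regression model to estimate the difference in the change from baseline between the two groups". It makes week 12 primary ("Least squares means for each outcome variable will be compared at the primary time point (week 12") and names no covariance structure. Visits are at "baseline, mid-intervention (6 weeks post-enrollment), and immediately following the intervention (12 weeks post-enrollment").

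Two other places bear on the remedy. Recruitment of SLE patients, repeated in section E under Recruitment and Informed Consent, has patients randomised after consent and lists the baseline questionnaires in what remains of that visit. Overview of Study Design instead compares patients who accept phone sessions with those who choose questionnaires only.

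**The concern.** Two separate matters arise from the same sentence.

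- **Precision.** A difference in raw change scores carries the full baseline noise. When baseline and week 12 correlate below 0.5, it is less precise than ignoring baseline altogether, and it is always less precise than adjusting for baseline. The planned correlation is 0.25.
- **Covariance.** A random subject effect with independent residuals makes every pair of visits equally correlated. AR(1) makes visits 12 weeks apart less correlated than visits 6 weeks apart. A model that averages the two understates the uncertainty of the week-12 change.

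Aim 2 exists to supply effect sizes and intervals for planning a later trial. An imprecise estimate, possibly with an interval that is too short, would pass straight into that sample size.

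**Working it through.** **Inputs.** n = 20 per arm, two-sided 95%, common SD taken as 1, three equally spaced visits and AR(1) with rho = 0.5 (all from the protocol). Hence the correlation is 0.5 between adjacent visits and 0.5² = 0.25 between baseline and week 12. Complete data are assumed. Week 12 is used as the endpoint, as in the Analysis Plan; the Sample Size Justification speaks of 12 months.

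**The plan's own figures.**
- Variance of change, baseline to week 12: 2(1 − 0.25) = 1.5.
- Within group: t(19) × √(1.5/20) = 0.573. This matches the stated 0.57, so the planners did work with a correlation of 0.25.
- Between groups on the same basis: t(38) × √(2 × 1.5/20) = 2.024 × 0.387 = 0.784. The stated 0.64 is instead t(38) × √(2/20) = 0.640, which needs a variance of 1. That would arise with a correlation of 0.5, with the SD of change as the unit, or from comparing week-12 means only.

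**Precision with baseline adjustment.**
- Residual variance at week 12 given baseline: 1 − 0.25² = 0.9375.
- Half-width: t(37) × √(2 × 0.9375/20) = 2.026 × 0.306 = 0.620. In simulation the mean half-width was 0.624 and coverage 95.1%.
- Variance ratio: 1.5/0.9375 = 1.6, as if there were 32 rather than 20 patients per arm.
- In general the ratio is 2(1 − r)/(1 − r²) = 2/(1 + r), where r is the baseline-to-week-12 correlation:

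| r | Change score | Adjusted | Ratio |
|---|---|---|---|
| 0.25 (planned) | 1.50 | 0.9375 | 1.60 |
| 0.50 | 1.00 | 0.75 | 1.33 |
| 0.70 | 0.60 | 0.51 | 1.18 |

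**Coverage if the subject effect is the only covariance term and the truth is AR(1), rho = 0.5.**
- The fitted residual variance has expectation 1 − (0.5 + 0.5 + 0.25)/3 = 0.583.
- The model therefore takes the variance of change as 2 × 0.583 = 1.167. The true value is 1.5 at week 12 and 1.0 at week 6.
- Ratio of model to true standard error at week 12: √(1.167/1.5) = 0.882. Coverage by the normal approximation: 2Φ(1.96 × 0.882) − 1 = 91.6%.
- In 150,000 simulated trials, between-group week-12 coverage was 91.2% (normal quantile), 91.6% (t, 76 df) and 92.1% (t, 38 df). The mean half-width with 76 df was 0.68, against the 0.78 this estimator needs.
- The within-group week-12 interval behaves alike (91.6%, 76 df). The week-6 interval over-covers (96.5%).
- Across rho, the normal approximation gives 92.9% at 0.3 and 90.0% at 0.8. If the true correlation is equal at all lags, coverage is 95.1%.

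With complete data the point estimate is the same under either covariance. The loss of precision therefore comes only from the free baseline means, and the under-coverage only from the covariance.

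**The case against.** **The covariance may not be fixed.** The protocol never says the residuals are independent. The paragraph can be read as a subject effect plus AR(1) within-subject correlation, and residual covariance is commonly left to the SAP, which is not shown. This stands. A reader might infer that the week-12 interval will cover only about 91–92%. The document does not support that as a fact: it needs both independent residuals and a true AR(1) pattern. What remains is that the listed terms cannot reproduce the correlation on which precision is planned, and the text does not say which is meant.

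**The model is valid, and adjustment is only more efficient.** This is also true. The stated model is unbiased under randomisation and gives the within-group changes directly. The gain of 60% holds only at the planned correlation. If the comparison of week-12 means is taken as the estimate, its variance is 1.0 and the gain is 1.0/0.9375, about 7%. But both Aim 2 passages name the difference in change as the target, and for that the loss is substantial on the plan's own assumption.

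**The remedy's preconditions are not met as written.** A reader might infer that equal baseline means can simply be imposed by rewording the analysis. The protocol does not support this. Baseline questionnaires are listed after randomisation. They are unblinded self-reports, and section E gives data collection to the lay navigator, whose role is to deliver the sessions. The Overview describes self-chosen groups, for which an equal-baseline constraint would be invalid. This objection stands and changes the fix.

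**It is a pilot without a hypothesis test on this interval.** That limits the consequence but does not remove it, since the estimate and its interval are what Aim 2 is meant to deliver.

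**Conclusion.** The point holds in two parts of unequal certainty.

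- **Firm:** as specified, the between-group effect is a raw difference in change scores. At the planned correlation its half-width is 0.78 SD, against 0.62 SD with baseline adjustment: a variance ratio of 1.6, falling to 1.33 at a correlation of 0.5 and 1.18 at 0.7. The 0.78 also exceeds the stated 0.64, while the adjusted analysis comes close to it.
- **Conditional:** if the subject effect is the only covariance term, it contradicts the planned AR(1), and week-12 coverage would be about 91–92%. With AR(1) residuals as well, there is no under-coverage and only the wording needs completing.

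Both rest on complete data, 20 per arm and week 12 as endpoint. The case for adjustment further rests on randomised allocation and on a baseline not influenced by knowledge of the arm, neither of which the protocol secures consistently. The change is worth making, but the present plan is not invalid.

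**What to change.** 1. Reconcile Overview of Study Design (patients choose) with Recruitment of SLE patients and section E, Recruitment and Informed Consent (patients are randomised). Have the baseline questionnaires completed before the allocation is revealed.
2. Estimate the between-group effect at weeks 6 and 12 with baseline LUP-QOL as a covariate, with its own slope at each visit (under the planned AR(1) the slopes would be 0.5 and 0.25). Do the same for PAM and SLAQ with their own baselines.
3. Keep the within-group change contrasts from the three-visit model.
4. State the covariance: unstructured over the visits, or at least one consistent with the planned AR(1), with small-sample degrees of freedom such as Kenward-Roger. If AR(1) residuals were meant all along, say so.
5. Use a common baseline mean for both arms only if allocation is randomised and baseline precedes its disclosure.
6. Restate the between-group precision for the analysis chosen.

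The cost is a few more covariance parameters to estimate from 40 patients and a reordering of steps within the recruitment visit. No new data or patients are needed.

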Our Intervention to Improve Quality of life for African-American lupus patients (IQAN) (ClinicalTrials.gov Identifier: NCT01837875) was an RCT that assigned 50 subjects each to one of three treatments groups: 1) a unique ‘a-la-carte’ self-management program with individualized intervention plan (IIP) including a mail-delivered arthritis kit, addition and access to a message board, participation in a support group, and enrollment in a local self-management program; 2) a ‘set menu’ that offered a standardized chronic disease self-management program only; and 3) a control group that received usual care (UC).[204] At 6 months of follow up, the ‘a-la-carte’ group had significant improvements in lupus disease activity, QOL, and stress/pain management compared to the control group. However, <50% of subjects completed intervention sessions and ~50% completed all follow-up assessments. Based on feedback from subjects in the BLESS study, the most valued aspect of the program was interaction with their peers, so the low completion rate in IQAN may have been due to absence of peer support.

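### The two Aim 2 precision figures are not on one stated basis: the inputs that give 0.57 SD within arm give 0.78 SD between arms, not 0.64 SD

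*Protocol*

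**What the plan says.** The Sample Size Justification in Section D supports Aim 2 by precision rather than power, in two consecutive sentences.

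- Within arm: 20 participants seen at three time points, with AR(1) correlation and rho = 0.5, "allows us to estimate a two-sided 95% confidence interval for change in LUP-QOL from baseline within group to within 0.57 standard deviations".
- Between arms: the next sentence opens "A sample size of 20 subjects per treatment group also allows us to estimate" and claims that the team can "estimate a 95% confidence interval for the difference in change in LUP-QOL from baseline between the two groups to within 0.64 standard deviations". The only assumption it adds is a common SD in the two groups. It names no other correlation, time point or unit.

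The Overview of Study Design puts the assessments at baseline, week 6 and week 12. The Aim 2 analysis plan makes week 12 the primary time point. The model has treatment, time and their interaction as fixed effects and a random subject effect. Baseline is not a covariate.

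**The concern.** Both figures describe the same contrast, change from baseline in LUP-QOL. The first is for one arm of 20 and the second for the difference between two such arms. The variance of a difference between two independent, equal-sized arms is twice the variance in one arm. The between-arm half-width should therefore exceed the within-arm one by a factor near √2. The stated figures differ by a factor of only 0.64/0.57 = 1.12.

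This paragraph is the numerical justification for the Aim 2 sample size. The Aim 2 heading says that the effect-size estimates are meant for sizing a later, larger trial. If 0.64 is read in the same unit as 0.57, the reader expects a tighter between-arm comparison than 20 per arm can give at week 12.

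**Working it through.** **Inputs** (protocol, Section D)

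- n = 20 per arm, all contributing data; two-sided 95% interval; common SD, set to 1.
- AR(1) with rho = 0.5. Week 12 is two steps from baseline, so r = 0.5² = 0.25.
- t quantiles: t(0.975, 19) = 2.093 and t(0.975, 38) = 2.024.

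**Step 1: reproduce the within-arm figure**

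Var(change) = 2(1 − r) = 2 × 0.75 = 1.5, so SD(change) = √1.5 = 1.2247.

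Half-width = 2.093 × √(1.5/20) = 0.573. This matches the stated 0.57.

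**Step 2: the between-arm figure on the same inputs**

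Half-width = 2.024 × √(2 × 1.5/20) = 0.784. The protocol states 0.64.

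Other quantiles do not close the gap: 0.759 with the normal quantile, 0.771 with 76 df and 0.811 with 19 df.

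**Step 3: a check that does not depend on the correlation**

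For any single correlation and unit, the ratio of between-arm to within-arm half-width is √2 × 2.024/2.093 = 1.37. Then 0.57 × 1.37 = 0.78. The stated ratio of 1.12 is below even √2.

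**Step 4: where 0.64 comes from**

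With SD(change) = 1, the half-width is 2.024 × √(2/20) = 0.640, which matches. SD(change) equals 1 if:

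- the unit is the SD of the change score; or
- baseline and follow-up correlate at 0.5, since 2(1 − 0.5) = 1. Under the stated AR(1) that is the week 6 correlation, not the week 12 one.

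An SD of 1 also applies to a comparison of week 12 values alone, or to the mean of weeks 6 and 12 minus baseline. Neither is the contrast described.

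On that basis the within-arm half-width is 2.093 × √(1/20) = 0.468, so the pair would be 0.47 and 0.64.

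**Step 5: correlation implied by each stated figure**

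Solving half-width = t × √(k × 2(1 − r)/20) for r, with k = 1 within arm and k = 2 between arms:

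- 0.57 within arm implies r ≈ 0.26.
- 0.64 between arms implies r ≈ 0.50.

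A 90% interval with the normal quantile at r = 0.25 gives 0.637, which also rounds to 0.64, but the protocol says 95%.

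**Summary (95% half-widths, n = 20 per arm)**

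| Basis | Within arm | Between arms |
|---|---|---|
| Outcome SD, r = 0.25 (AR(1), week 12) | 0.57 | 0.78 |
| SD of change, or r = 0.5 | 0.47 | 0.64 |
| As stated | 0.57 | 0.64 |

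The stated pair takes one figure from each row.

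**The case against.** The strongest defence is that the AR(1) assumption belongs to the within-arm sentence only. The between-arm sentence brings in the usual two-sample condition of a common SD, and the textbook two-sample formula gives 0.640. If its unit is the SD of the change, then 0.64 × √1.5 = 0.784 outcome SDs. That is the same interval in another unit, and only a label is missing.

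Part of this stands. The number 0.64 is not impossible in itself, so a reader who infers that the two figures cannot both be true under any reading goes too far. They conflict only on one common basis. But the protocol announces no change of basis. The second sentence continues the first with the word also and uses the same term, standard deviations. A reader will take both figures in one unit, and in that unit they do not agree.

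A reader might also infer a larger loss of precision from attrition. Section C reports that in the group's earlier three-arm trial "<50% of subjects completed intervention sessions and ~50% completed all follow-up assessments". The documents do not support a specific figure here. Completing every assessment is not the same as staying in the trial. The protocol suggests that the earlier result may reflect a lack of peer support, and estimating drop-out is itself part of Aim 1. A formula that counts completers only would also not match the planned mixed model, which uses the earlier visits of participants without week 12 data.

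**Conclusion.** Wrong as written; minor to moderate. On the protocol's own inputs the between-arm half-width is 0.78 SD, 22% wider than 0.64 (0.784/0.640 = 1.22). In outcome-SD units, a half-width of 0.64 would need about 30 per arm: with t(0.975, 58) = 2.002, 2.002 × √(3/30) = 0.63.

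The result assumes that:

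- both figures are in SDs of the outcome;
- the contrast is baseline to week 12. The Sample Size Justification speaks of 12 months after the intervention, but the visit schedule and the primary time point are week 12, and 0.57 fits the third of three visits;
- all 20 per arm contribute data, as the protocol's own figures assume.

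A reader might infer that the sample size is inadequate or the Aim 2 analysis compromised. The documents do not support that. This is an estimation pilot: no Aim 2 test, success threshold or enrolment rule uses 0.64, and the reported intervals will have whatever width the data give. What is misstated is the precision planned in advance, in the favourable direction.

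**What to change.** Put both figures in the Sample Size Justification on one stated basis. Either:

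1. Keep 0.57 and replace 0.64 with 0.78, saying that both are in SDs of the LUP-QOL score for the change from baseline to week 12 under AR(1) with rho = 0.5. This fits the assumptions already printed.
2. If SD-of-change units or a baseline-to-follow-up correlation of 0.5 was intended, say so and give 0.47 within arm and 0.64 between arms.

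The cost is one sentence. Under the first option the stated between-arm precision becomes less favourable. Enrolment, visits and analysis model stay as they are.
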